6.4 EXPLORATORY EFFICACY ENDPOINTS

6.4.1 DICHOTOMOUS OR BINARY ENDPOINTS

The definition of the binary exploratory endpoints are listed in Table 4 below.

Table 4 Definition of Exploratory Binary Endpoints

Outcome	Measure	Definition	Analysis Timepoints
Endoscopic Remission	SES-CD	SES-CD ≤ 4 and at least 2-point reduction from baseline and all individual score ≤ 1	Week 12
Ulcer-free	SES-CD (Ulcerated Surface)	SES-CD ulcerated surface score of 0, among patients with SES-CD ulcerated surface score ≥ 1 at baseline	Week 12
Clinical response by PRO-2	PRO-2	$\geq 30\%$ reduction of either score and no worsening in both scores	Over time
Clinical response by PRO-2 total score	PRO-2	$\geq 30\%$ reduction of PRO-2 total score	Over time
Enhanced Clinical response by PRO-2	PRO-2	reduction of $\geq 60\%$ in average daily stool frequencies or a reduction of $\geq 35\%$ in average daily abdominal pain score, and no worsening in both score	Over time
Enhanced Clinical response and Endoscopic improvement	PRO-2 and SES-CD	enhanced clinical response by PRO-2 score and endoscopic improvement	Week 12
IBDQ Remission	IBDQ	IBDQ total score of >170	Week 12
IBDQ Rresponse	IBDQ	≥ 16 -point increase from baseline or an absolute score of >170	Week 12
Improvement or remission of enterocutaneous and/or perianal fistula	Fistula	Fistula Improvement from baseline among patients with fistula at baseline	Week 12
GHAS histologic remission	GHAS	No neutrophils in the epithelium or subscore of 0	Week 12
GHAS histologic response	GHAS	GHAS histologic score ≤ 4	Week 12
Robarts histologic remission	RHI	RHI < 3	Week 12
Robarts histologic response	RHI	Robarts histologic score < 5	Week 12

Abbreviations: SES-CD, Simple endoscopy score for Crohn's disease; CDAI, Crohn's disease activity index; hsCRP, High sensitivity C-reactive protein; PRO-2, Two component patient-reported outcome; GHAS, Global histological activity score; RHI, Robarts histopathology index; IBDQ, Inflammatory Bowel Disease Questionnaire.

The proportion of subjects of meeting the definition of these endpoints will be calculated in FAS, though patients with missing data will be excluded from the summary.

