## 4 INVESTIGATIONAL PLAN

### 4.1 Study Design

This is a multi-center, open-label, proof of concept study designed to assess the safety, tolerability, and preliminary efficacy of PRA023 following 12 weeks of induction therapy in subjects with CD. This study will be conducted under the aegis of a DMC and will commence following the demonstration of an acceptable safety profile of PRA023 at a dose of  $\geq 500$  mg in the multiple ascending dose study in normal healthy volunteers (Study PR200-101).

The study has 4 periods (Screening, IP, OLE, and FU Period). An ileocolonoscopy must be performed during the Screening Visit between 28 to 10 days prior to the Week 0/Day 1.

Following the Screening Period, approximately 50 eligible subjects with moderately to severely active CD will enter the IP to receive PRA023 1000 mg on Week 0/Day 1, followed by 500 mg on Weeks 2, 6, and 10 via IV administration. Subjects who discontinue from the study drug will have a follow-up period of 12 weeks after the last dose.

Response at Week 12 will be defined as reduction from Baseline in CDAI of  $\geq 100$  points. Non-responders at Week 12 should be discontinued from study drug treatment.

[figure not shown]
Subjects who complete the 12-week IP and have responded will have the option to enter OLE, where they will be randomized to either 250 mg IV Q4W or 100 mg IV Q4W until Week 134. Subjects will continue in OLE until they progress, withdraw from the study, study termination, or Week 134.

The study may be amended by the Sponsor to extend the OLE beyond 134 weeks based on emerging safety data.

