### 8.2 Justification of Sample Size

The planned sample size is 50 subjects, which will provide a statistical power of 80% to test against the null hypothesis of endoscopic improvement rate of 12%, at 1-sided significance level of 0.025, assuming the endoscopic improvement rate for PRA023 is 27%.

The null hypothesis of an endoscopic improvement (decrease in SES-CD  $\geq$  50%) rate of 12% is based on a meta-analysis estimate of the upper limit of 95% CI of the observed placebo rate (95% CI) of 9.5% (7.1, 11.9) from multiple modern-era CD clinical trials with centrally read endoscopy and similar eligibility criteria ([Table 7](#)).

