3.2 DETERMINATION OF SAMPLE SIZE

The study is planned to enroll approximately 50 subjects. The sample size will enable a statistical power of 80%, at 1-sided significance level of 0.025, to test against the null hypothesis of endoscopic improvement rate of 12%, assuming the endoscopic improvement rate for PRA023 is 27%.

The null hypothesis of an endoscopic improvement (decrease in SES-CD $\geq 50\%$) rate of 12% is based on a meta-analysis estimate of the upper limit of 95% CI of the observed placebo rate (95% CI) of 9.5% (7.1, 11.9) from multiple modern-era CD clinical trials with centrally read endoscopy and similar eligibility criteria. [1]

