6.4.2 CONTINUOUS EFFICACY ENDPOINTS

The definition of the continue efficacy endpoints (Mean Change from Baseline) by visit are listed in Table 5 below.

Table 5 Definition of Exploratory Continuous Endpoints

Measure	Definition	Analysis Timepoint
SES-CD segment score	Mean change from baseline	Week 12
PD markers (TL1A concentrations, fecal calprotectin, and hsCRP)	Mean fold change from baseline	Over time
RHI	Mean change in Roberts Histopathology Index (RHI) from baseline	Week 12
GHAS	Mean change in global histological activity score (GHAS) from baseline	Week 12
PDAI	Mean change in Perianal Disease Activity Index(PDAI) subscore from baseline	Week 12
CDAI	Mean change in CDAI and components from Baseline over time	Over time
PRO-2	Mean change in PRO-2 over time	Over time
IBDQ	Mean change from baseline in IBDQ score over time	Over time

Abbreviations: CDAI, Crohn's disease activity index; hsCRP, High sensitivity C-reactive protein; PRO-2, Two component patient-reported outcome; RHI, Roberts Histopathology Index; GHAS, Global histological activity score; SES-CD, Simple endoscopy score for Crohn's disease; PDAI, Perianal Disease Activity Index; IBDQ, Inflammatory Bowel Disease Questionnaire.

In general, continuous endpoints will be summarized using descriptive statistics of the values at each visit and the change from baseline to each post-baseline visit. Missing data will not be imputed for descriptive statistics.

The mean change in CDAI over time through Week 12, mean change in PRO-2 over time through Week 12 and mean change in IBDQ score over time through Week 12 will be estimated according to a MMRM model with baseline CDAI, visit as fixed effect and subject as random effect. The 95% confidence intervals at each time point will be calculated according to the MMRM model. This analysis will be conducted by maximum likelihood methods using the SAS PROC MIXED procedure.

Additional descriptive summary over time will be reported for patients who entered OLE based on available data as of cutoff date of the DBL for Induction period.

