6.8 MISSING DATA HANDLING

6.8.1 NON-RESPONDER IMPUTATION (NRI)

For the responder analyses as described in Table 3 of Section 6.2, unless specified otherwise, subjects who do not have sufficient measurements to determine the endpoint will be considered as non-responders (i.e., non-responder imputation (NRI)). Specifically, all subjects who discontinue from the study at any time prior to the assessment timepoint (regardless of reason) or fail to have an adequate efficacy assessment at that timepoint will be considered a non-responder.

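### Exploratory response rates in SAP Table 4 drop subjects with missing data from the FAS denominator, while the Table 3 rates at the same Week 12 visit count them as non-responders

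*SAP*

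**What the plan says.** **Exploratory binary endpoints.** SAP Table 4 lists 13. Under SAP 6.4.1 their proportions "will be calculated in FAS, though patients with missing data will be excluded from the summary". Table 4 gives the timepoint as over time for three of them, all based on PRO-2 (clinical response, response by total score, enhanced response). The other ten are at Week 12. (SAP Table 1 words the fistula endpoint as over time, whereas Table 4 has it at Week 12.)

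**Secondary binary endpoints.** SAP 6.3.1 imputes missing values as non-response in the FAS. SAP 6.8.1 restates this for Table 3 only. Its rule covers "all subjects who discontinue from the study at any time prior to the assessment timepoint (regardless of reason"), and anyone without an adequate assessment at the timepoint. SAP 4.3 makes no imputation the default for descriptive statistics. Nothing in the SAP extends the 6.8.1 rule to Table 4.

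**Interim OLE data.** SAP Section 6 promises a descriptive summary of selected, unnamed efficacy endpoints. SAP 6.4.2 adds: "Additional descriptive summary over time will be reported for patients who entered OLE based on available data as of cutoff date". Neither gives a denominator. Subjects who do not respond by CDAI at Week 12 should stop study drug, so entrants are Week 12 responders (Protocol 4.1, SAP 3.1). The exit rule is "Subjects will continue in OLE until they progress, withdraw from the study, study termination, or Week 134". SAP 3.1, written against protocol version 3.0, has the same rule ending at Week 50.

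**The concern.** A subject who leaves before Week 12 without an assessment is a failure in Table 3 and absent from Table 4, yet both tables are described as FAS results. Two pairs show the clash. PRO-2 remission uses NRI, and PRO-2 response at the same visit uses observed cases. The composite of endoscopic and clinical improvement uses NRI, and the composite of enhanced clinical response and endoscopic improvement uses observed cases. SAP Section 10 gives no reason for the difference.

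The direction matters because treatment failure is a written way out of the study. Protocol 4.4.6 permits rescue only during the OLE and has subjects who need a new Crohn's therapy withdrawn. Protocol 4.5 requires discontinuation on biologic therapy for Crohn's disease. OLE participation ends on progression. With no concurrent control arm, nothing else in the output would reveal how far attrition shapes a response rate. Interim OLE summaries add a further ambiguity: a visit not yet due at the cutoff and a visit missed because the subject left are both simply unavailable.

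**Working it through.** **The plan's own figure.** The documents state no expected value for any Table 4 or OLE rate. The nearest figure is the sample size in Protocol 8.2: "The planned sample size is 50 subjects, which will provide a statistical power of 80"%. Its inputs are a 12% null rate, a 27% rate on PRA023 and a one-sided alpha of 0.025. A continuity-corrected normal approximation at N = 50 gives a power of Φ((0.15 − 0.01 − 1.96 × √(0.12 × 0.88/50)) / √(0.27 × 0.73/50)) = Φ((0.14 − 0.0901)/0.0628) = 78.7%, close to the stated 80%. This does not bear on the point. It only supports 50 as a working denominator.

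**The built-in gap.** For one endpoint at one visit, let N be the eligible FAS subjects, m those with no assessment and R the observed responders.

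- Observed-case rate (6.4.1) = R/(N − m)
- NRI rate (6.8.1) = R/N
- Ratio = N/(N − m), whatever R is

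At N = 50: m = 5 gives 50/45 = 1.11, m = 10 gives 50/40 = 1.25, and m = 15 gives 50/35 = 1.43. This takes R to be the same under both rules.

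**Which rate is nearer the truth.** Suppose 40% (20 of 50) would respond if all were assessed, and missing subjects respond at rate q. Then R = 20 − q × m. Both the 40% and q are assumptions. Cells show observed-case / NRI, in percent.

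| q | m = 0 | m = 5 | m = 10 | m = 15 |
|---|---|---|---|---|
| 0% | 40.0 / 40.0 | 44.4 / 40.0 | 50.0 / 40.0 | 57.1 / 40.0 |
| 20% | 40.0 / 40.0 | 42.2 / 38.0 | 45.0 / 36.0 | 48.6 / 34.0 |
| 40% | 40.0 / 40.0 | 40.0 / 36.0 | 40.0 / 32.0 | 40.0 / 28.0 |
| 60% | 40.0 / 40.0 | 37.8 / 34.0 | 35.0 / 28.0 | 31.4 / 22.0 |

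The observed-case rate is too high when q is below 40%, right at 40% and too low above it. NRI is right when no missing subject would have responded and too low otherwise.

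**Over time.** The gap can widen across visits only where an endpoint is reported at several visits. In Table 4 those are the three PRO-2 endpoints.

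**Interim OLE.** Assume 25 of 50 enter, 5 progress and leave, and 20 still respond by CDAI. Available-case response is 20/20 = 100%. With the 5 counted as non-responders it is 20/25 = 80% of entrants. On the FAS it is 20/50 = 40%. Since entrants start at 100%, the loss of progressors can keep the available-case figure near 100%.

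**The case against.** The case for leaving the plan alone is fair.

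- **The rule is open and prespecified**, for endpoints outside the testing hierarchy of SAP 6.10. No decision depends on them.
- **NRI has its own bias.** In the table's third row, with 15 missing, it reports 28% where the truth is 40% and the observed-case rate is right. An unreadable biopsy or a diary gap is not a treatment failure. PRO-2 is missing whenever fewer than five evaluable days can be found in ten (SAP 6.1.2), which can be intermittent.
- **Other analyses cover much of this ground.** The Table 3 endpoints use NRI, endoscopic improvement has an FAS analysis with missing counted as non-response (SAP 6.2.2), and mean CDAI, PRO-2 and IBDQ change through Week 12 is modelled by MMRM.
- **Stopping does not always mean missing data.** Protocol 4.5 asks for end-of-study evaluations at withdrawal, and SAP Table 2 has a Week 12/ET visit.
- **The OLE is mostly out of scope.** SAP Section 9 defers its full analysis to another SAP, the 6.4.1 sentence does not govern it, and the 6.4.2 sentence sits among continuous endpoints and names no responder rate.

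Most of this stands as a limit on importance. It does not remove the inconsistency: none of it explains why similar Week 12 endpoints follow different rules. The MMRM does not estimate response proportions, and one early-termination assessment cannot fill every later visit. The conservatism of NRI is a reason to show both rates.

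**Conclusion.** The point holds as an inconsistency in denominators. All 13 Table 4 rates exceed their own NRI rates by N/(N − m) whenever there are responders and missing data: 1.11, 1.25 and 1.43 at 10%, 20% and 30% missing. Those shares are assumed. They are also biased upward to the extent that subjects stop for lack of effect, which the withdrawal rules make likely but not certain.

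A reader might infer that response will rise with time on drug by construction. The documents do not support that. Only the excess over NRI is arithmetic. With a constant 40% underlying rate and 20% missing, the observed-case rate is 50%, 45%, 40% or 35% as missing subjects respond at 0%, 20%, 40% or 60%. Ten of the 13 endpoints have a single timepoint in Table 4 and cannot drift.

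A reader might also expect interim OLE response to climb as failures leave. CDAI response cannot, because entrants begin at 100%. The risk there is a curve held near 100%. That OLE point rests on SAP Section 6 and 6.4.2, and applies only if a binary endpoint is among those selected.

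Priority is low: the endpoints are exploratory, descriptive and untested.

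**What to change.** 1. In SAP 6.4.1, apply the 6.8.1 rule to every Table 4 binary endpoint in the FAS, within the baseline-eligible subset where one is stated (ulcer-free, fistula). Keep the observed-case rate as supporting, and show number assessed over N at each visit.
2. In SAP 6.8.1, extend the stated scope from Table 3 to Tables 3 and 4.
3. For any interim OLE binary summary, take as denominator the OLE entrants whose visit window had closed by the data cutoff. Count those who discontinued earlier as non-responders, and show entered, due, discontinued and assessed at each visit. Applying NRI to all entrants would wrongly turn visits not yet due into failures.

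The cost is SAP wording and minor programming, with no new data and no change in conduct. Exploratory rates will look somewhat less favourable, and NRI will understate response where data are missing for reasons unrelated to treatment. The supporting observed-case rates and the printed counts let the reader judge that.

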6.4.2 CONTINUOUS EFFICACY ENDPOINTS

The definition of the continue efficacy endpoints (Mean Change from Baseline) by visit are listed in Table 5 below.

Table 5 Definition of Exploratory Continuous Endpoints

Measure	Definition	Analysis Timepoint
SES-CD segment score	Mean change from baseline	Week 12
PD markers (TL1A concentrations, fecal calprotectin, and hsCRP)	Mean fold change from baseline	Over time
RHI	Mean change in Roberts Histopathology Index (RHI) from baseline	Week 12
GHAS	Mean change in global histological activity score (GHAS) from baseline	Week 12
PDAI	Mean change in Perianal Disease Activity Index(PDAI) subscore from baseline	Week 12
CDAI	Mean change in CDAI and components from Baseline over time	Over time
PRO-2	Mean change in PRO-2 over time	Over time
IBDQ	Mean change from baseline in IBDQ score over time	Over time

Abbreviations: CDAI, Crohn's disease activity index; hsCRP, High sensitivity C-reactive protein; PRO-2, Two component patient-reported outcome; RHI, Roberts Histopathology Index; GHAS, Global histological activity score; SES-CD, Simple endoscopy score for Crohn's disease; PDAI, Perianal Disease Activity Index; IBDQ, Inflammatory Bowel Disease Questionnaire.

In general, continuous endpoints will be summarized using descriptive statistics of the values at each visit and the change from baseline to each post-baseline visit. Missing data will not be imputed for descriptive statistics.

The mean change in CDAI over time through Week 12, mean change in PRO-2 over time through Week 12 and mean change in IBDQ score over time through Week 12 will be estimated according to a MMRM model with baseline CDAI, visit as fixed effect and subject as random effect. The 95% confidence intervals at each time point will be calculated according to the MMRM model. This analysis will be conducted by maximum likelihood methods using the SAS PROC MIXED procedure.

Additional descriptive summary over time will be reported for patients who entered OLE based on available data as of cutoff date of the DBL for Induction period.

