### 2.3 Exploratory Objectives

- To assess the change in CDAI and component scores over time
- To assess the effects of PRA023 on tissue and serum PD markers, including TL1A concentrations, endoscopic healing index (EHI), fecal calprotectin, and hsCRP in all subjects over time
- To assess the change in SES-CD at Week 50 from Baseline

- To characterize the change in PDAI score from Baseline to Week 12, Week 28 and Week 50
- To characterize the effect of PRA023 for improvement and remission of enterocutaneous and/or perianal fistula during the Induction Period (IP) and Open-Label Extension (OLE)
- To assess all secondary endpoints at Week 50
- To assess the change in GHAS and RHI from Baseline to Week 12 and Week 50
- To assess the proportion of subjects with histologic response and histologic remission at Week 12 and Week 50
- To assess the change in PRO-2 over time
- To assess the change in extraintestinal manifestations over time
- To assess long-term safety, tolerability, and efficacy of PRA023

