### 16.3 Perianal Disease Activity Index (PDAI)

The perianal disease activity index (PDAI) score includes the evaluation of 5 elements:

1. discharge
2. pain
3. restriction of sexual activity
4. type of perianal disease
5. degree of induration

Each category is graded on a 5-point Likert scale ranging from no symptoms (score of 0) to severe symptoms (score of 4), with a range of 0 to 20; a higher score indicates more severe disease.

Item	Points
Discharge	
No discharge	0
Minimal mucous discharge	1
Moderate mucous or purulent discharge	2
Substantial discharge	3
Gross fecal soiling	4
Pain/restriction of activities	
No activity restriction	0
Mild discomfort, no restriction	1
Moderate discomfort, some limitation	2
Marked discomfort, marked limitation	3
Severe pain, severe limitation	4
Restriction of sexual activity	
No restriction of sexual activity	0
Slight restriction of sexual activity	1
Moderate limitation of sexual activity	2
Marked limitation of sexual activity	3
Unable to engage in sexual activity	4
Type of perianal disease	
No perianal disease	0
Anal fissure or mucosal tear	1
<3 perianal fistulas	2
>3 perianal fistulas	3
Anal sphincter ulceration or fistulas with significant undermining skin	4
Degree of induration	
No induration	0
Minimal induration	1
Moderate induration	2
Substantial induration	3
Gross fluctuance/abscess	4

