To assess the clinical improvement by PRO-2 score at Week 12	
 Change in PRO-2 over time Proportion of subjects with clinical improvement by PRO-2 score, defined as \geq 30% reduction of either score and no worsening in both scores at Week 12 Proportion of subjects with enhanced clinical response by PRO-2 score, defined as a reduction of \geq 60% in average daily stool frequency or a reduction of \geq 35% in average daily abdominal pain score, and no worsening in both scores at Week 12 Proportion of subjects with \geq 30% reduction of PRO-2 total score
To assess the proportion of subjects with both clinical improvement and endoscopic improvement at Week 12	
 Proportion of subjects who achieve both enhanced clinical response by PRO-2 score and endoscopic improvement at Week 12
To assess the IBDQ remission or IBDQ improvement at Week 12	
 Proportion of subjects with IBDQ remission or IBDQ improvement at Week 12
To assess the change from baseline in IBDQ scores at Week 12	
 Change from baseline in IBDQ scores
To assess the change in CDAI and component scores over time	
 Change in CDAI and components from Baseline over time

To assess the effects of PRA023 on tissue and serum pharmacodynamic (PD) markers, including tumor necrosis factor-like cytokine 1A (TL1A) concentrations, fecal calprotectin, and hsCRP in all subjects over time	
 • Change in PD markers including TL1A concentrations, fecal calprotectin, and hsCRP over time
To characterize the change in Perianal Disease Activity Index (PDAI) score from Baseline to Week 12	
 • Change in PDAI from Baseline over time
To characterize the effect of PRA023 for improvement and remission of enterocutaneous and/or perianal fistula -Overtime	
 • Proportion of subjects with improvement or remission of enterocutaneous and/or perianal fistula Overtime , among patients with fistula at baseline
To assess the change in global histological activity score (GHAS) and Roberts histopathology index (RHI) from Baseline to Week 12	
 • Change in mean GHAS and RHI scores from Baseline to Week 12 • Proportion of subjects with GHAS histologic score ≤ 4 at Week 12 • Proportion of subjects with Roberts histologic score < 5 at Week 12

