4.2.3 FULL ANALYSIS SET (FAS)

All subjects who have been treated with PRA023 with Baseline CDAI and SES-CD scores will be included in the FAS. The FAS set will be used for efficacy analysis.

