6 EFFICACY ANALYSES

Efficacy analyses for IP will primarily be based on the FAS, and supportive efficacy analysis will be based on PP, unless specified otherwise. Demographic data characteristics (height, weight, age, sex, race, and ethnic origin) will be listed by subject and summarized by CDx status and for the overall study population. Selected efficacy endpoints over time during the OLE will be summarized descriptively.

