APPENDIX D. PERIANAL DISEASE ACTIVITY INDEX (PDAI)

The perianal disease activity index (PDAI) score includes the evaluation of 5 elements:

- 1) discharge
- 2) pain
- 3) restriction of sexual activity
- 4) type of perianal disease
- 5) degree of induration

Each category is graded on a 5-point Likert scale ranging from no symptoms (score of 0) to severe symptoms (score of 4), with a range of 0 to 20; a higher score indicates more severe disease.

Item	Points
Discharge	
No discharge	0
Minimal mucous discharge	1
Moderate mucous or purulent discharge	2
Substantial discharge	3
Gross fecal soiling	4
Pain/restriction of activities	
No activity restriction	0
Mild discomfort, no restriction	1
Moderate discomfort, some limitation	2
Marked discomfort, marked limitation	3
Severe pain, severe limitation	4
Restriction of sexual activity	
No restriction of sexual activity	0
Slight restriction of sexual activity	1
Moderate limitation of sexual activity	2
Marked limitation of sexual activity	3
Unable to engage in sexual activity	4
Type of perianal disease	
No perianal disease	0
Anal fissure or mucosal tear	1
<3 perianal fistulas	2
>3 perianal fistulas	3
Anal sphincter ulceration or fistulas with significant undermining skin	4
Degree of induration	
No induration	0
Minimal induration	1
Moderate induration	2
Substantial induration	3
Gross fluctuance/abscess	4

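### The Week 12 PDAI mean pools in subjects who had no perianal disease at baseline, which dilutes it; the score also has no category for exactly three fistulas

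*SAP*

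**What the plan says.** **Endpoint.** SAP section 6.4.2, Table 5, gives the PDAI endpoint as "Mean change in Perianal Disease Activity Index(PDAI) subscore from baseline", with Week 12 as the timepoint and no condition on baseline status. The summary is descriptive (SAP 4.1 lists mean, median and SD among the statistics) and missing values are not imputed. PDAI is not among the endpoints given a repeated-measures model.

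**Population.** SAP section 6 sets the default: "Efficacy analyses for IP will primarily be based on the FAS". SAP 4.2.3 defines that set: "All subjects who have been treated with PRA023 with Baseline CDAI and SES-CD scores will be included in the FAS". Perianal disease is not required. The induction schedule (Protocol Table 2, SAP Appendix G) has PDAI at Week 0, Week 12 and early termination for all subjects.

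**Comparable endpoints.** The SAP does restrict other endpoints to subjects who are abnormal at baseline. The fistula row of Table 4 reads "Fistula Improvement from baseline among patients with fistula at baseline", and SAP Table 1 has the same limit ("among patients with fistula at baseline"). Ulcer-free status and normalization of hsCRP and fecal calprotectin are restricted in the same way.

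**Scoring.** SAP 6.1.3 and Appendix D, and Protocol 6.4.3 and 16.3, describe five items of 0 to 4, totalling 0 to 20. No subscore is defined. In both appendices the disease-type item gives 2 points for "<3 perianal fistulas" and 3 points for ">3 perianal fistulas".

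**Timepoints.** Protocol 2.3 has the objective "To characterize the change in PDAI score from Baseline to Week 12, Week 28 and Week 50", and the synopsis names the same weeks. Protocol Table 3 schedules PDAI at Weeks 26 and 50. The SAP objective names Week 12 only.

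**The concern.** A subject with no perianal disease sits at the floor of the scale and has no room to improve. If most of the FAS is in that position, the reported mean mostly reflects how many subjects had perianal disease, and only secondarily how much they changed. A small mean could be a useful change in a few subjects or a trivial change in many, and Table 5 does not call for the n that would separate the two.

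Three smaller matters affect the same endpoint. The word *subscore* leaves open what is averaged. A subject with exactly three perianal fistulas fits neither category of the disease-type item, and PDAI has no rule for a missing item, whereas SES-CD, CDAI and IBDQ each have one. The protocol objective also names a week at which PDAI is not collected.

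At stake is the usefulness of one exploratory summary. No primary or secondary conclusion depends on it.

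**Working it through.** The documents give no sample size, power, SD or expected change for PDAI, so there is no planned figure to reproduce.

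**Inputs.** N = 50 (Protocol 8.2, SAP 3.2). Scale 0 to 20 (SAP 6.1.3). The share affected at baseline, *q*, is not given; I assume a range of 10% to 50%. Mean change in affected subjects *d* = −3 and SD *s* = 3 are illustrative assumptions. Unaffected subjects are assumed to start at 0 and stay there.

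**Formulas.**
- All-subject mean = *q·d*
- All-subject SD = √(*q·s²* + *q*(1 − *q*)·*d²*)
- Standardized change = |mean| / SD; for affected subjects alone it is 3/3 = 1.00
- |mean|/SE = standardized change × √n, with n = 50 for all subjects and n = 50*q* for affected subjects

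Example at *q* = 0.20: mean = 0.2 × (−3) = −0.60. Variance = 0.2 × 9 + 0.2 × 0.8 × 9 = 1.80 + 1.44 = 3.24, so SD = 1.80. Standardized change = 0.60/1.80 = 0.33.

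| Share affected (n) | All-subject mean | All-subject SD | Standardized, all | Standardized, affected | mean/SE, all | mean/SE, affected |
|---|---|---|---|---|---|---|
| 10% (5) | −0.30 | 1.31 | 0.23 | 1.00 | 1.62 | 2.24 |
| 20% (10) | −0.60 | 1.80 | 0.33 | 1.00 | 2.36 | 3.16 |
| 30% (15) | −0.90 | 2.14 | 0.42 | 1.00 | 2.97 | 3.87 |
| 40% (20) | −1.20 | 2.40 | 0.50 | 1.00 | 3.54 | 4.47 |
| 50% (25) | −1.50 | 2.60 | 0.58 | 1.00 | 4.08 | 5.00 |

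With a larger assumed change of −5 (SD 3), the all-subject mean runs from −0.50 to −2.50 and the standardized change from 0.28 to 0.76, against 1.67 in affected subjects. The pattern is the same.

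**Median.** If fewer than half the subjects are affected, the unaffected stay at 0, and the affected improve or stay unchanged, then more than half the changes are exactly 0 and none is positive. The median change is 0 however large the improvement.

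**Absolute precision.** At *q* = 20% the SE of the all-subject mean is 1.80/√50 = 0.25, and that of the restricted mean is 3/√10 = 0.95. The restricted estimate has the wider interval but the better ratio of mean to SE.

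**Fistula count.** The gap lies between 2 and 3 points on one item, so it is worth 1 point of 20 in an affected subject. Among 10 affected subjects, one such difference moves the mean by 1/10 = 0.1.

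**Week 28.** Study day = 7 × week + 1, so Week 26 is Day 183 and its ±14-day window is Days 169 to 197. Week 28 is Day 197. Infusions every 4 weeks from Week 14 fall at Weeks 18, 22, 26 and 30. Week 28 is therefore neither an office visit nor an infusion visit, though it is the last day of the Week 26 window.

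**The case against.** The strongest reply is that the all-subject mean is a legitimate summary. It answers a question about the whole treated population and counts new perianal disease, which a restricted analysis misses. Selecting subjects with PDAI above 0 in a single-arm study invites regression to the mean and so favours apparent improvement. This stands, and it is a reason to show both summaries rather than replace one with the other.

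A second reply is that the fistula endpoint already covers affected subjects. That is only partly so. Protocol 6.4.4 counts draining fistulas, while PDAI also covers pain, sexual restriction, fissure, ulceration and induration.

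A third is that the figures rest on assumptions. They do: prevalence, change and SD are all assumed, unaffected subjects are taken to have zero change, and no test on PDAI is planned. The mean/SE columns show relative signal only. The proportional dilution itself does not depend on *d* or *s*.

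A reader might infer more than the documents support:

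- *That the endpoint cannot show a perianal effect.* The table shows otherwise: mean/SE is 2.36 at 20% affected and 3.54 at 40%.
- *That pooling worsens precision.* The all-subject SE is the smaller one, 0.25 against 0.95. What falls is the signal relative to noise.
- *That Week 28 undermines the SAP analysis.* Table 5 uses Week 12, when PDAI is collected. Week 28 appears only in the protocol objective. Protocol section 6 lets the schedule tables override the text, and SAP section 9 leaves the complete extension analysis to another SAP.
- *That the fistula gap makes the score unusable.* It touches only subjects with exactly three perianal fistulas, an unknown and possibly zero number.

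**Conclusion.** The point holds as a minor one. As written, the Week 12 PDAI mean includes FAS subjects at the scale floor, so it shrinks toward zero in proportion to the unaffected share and is hard to interpret without knowing that share. At an assumed 10% to 50% affected, the all-subject mean is 10% to 50% of the affected-subject mean. With an illustrative change of −3 (SD 3), the standardized change drops from 1.00 to between 0.23 and 0.58. If some unaffected subjects worsen, the mean moves further from the affected-subject change.

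The unrestricted form also departs from the SAP's own handling of fistula, ulcer-free status and biomarker normalization. The undefined subscore and the missing category for three fistulas are real drafting gaps of small effect. The Week 28 reference is a slip in the protocol objective, with no bearing on the induction analysis.

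**What to change.** In SAP Table 5:

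- Report PDAI change at Week 12 among subjects with baseline PDAI above 0, and show n.
- Keep the all-subject summary, or list new perianal disease separately, so that worsening from 0 stays visible.
- State whether the total score or subscores are analysed.
- Note that the restricted group may show regression to the mean and that there is no control group.

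In SAP Appendix D and Protocol 16.3, assign exactly three perianal fistulas to one category after checking the source instrument, and apply it to data already scored.

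In the protocol synopsis and section 2.3, reconcile Week 28 with the scheduled Week 26 assessment.

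The cost is wording in the SAP and the protocol. No new visits or data are needed beyond checking any subject recorded with three fistulas. The price of the restricted summary is a smaller n and a wider interval: 10 subjects and an SE of 0.95 in the 20% illustration.
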